3.4.2.5 Study Visit 4 - Day 12 (+/- 3 days)

- Check on occurrence of adverse events.
- Perform fungal scrapings for mycological culture as instructed by the laboratory.
- Photograph the treated nail.

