2.0 STUDY OBJECTIVES

The purpose of this study is to assess the clinical feasibility of DeviceFarm, Inc.'s RenewalNail™ system and the treatment protocol that was developed based on extensive laboratory testing on human cadaver nails.

The primary objective of this study is to evaluate the efficacy and safety of the RenewalNail™ plasma treatment system and Protocol in achieving mycological cure for the patient. The Protocol calls for three 45-minute treatments performed over a week to achieve mycological cure. Mycological cure will be assessed with two consecutive mycological culture tests done over a week. Two consecutive negative mycology culture results confirm the elimination of fungus causing onychomycosis infection, as recommended by recent FDA guidance. There will be no placebo arm in the study.

Secondary objectives include:

- Will the treatment protocol result in clear nail growth for the patient over a 5-month interval?
- Is the instrument functional in a clinical setting as related to user instructions, user interface and human factor analysis?
- Are there treatment protocol or instrument changes that would improve the treatment results, patient safety, or patient comfort?
- Are there fungal species beyond *Trichophyton rubrum* and *Trichophyton mentagrophytes* that are not affected by the treatment, as seen in species identification from the nail scrapings?

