3.0 INVESTIGATIONAL PLAN

3.1 Overall Study Design

DeviceFarm, Inc.'s Early Feasibility Study will be conducted as a Single-center open-label study in Subjects who meet the specified inclusion/exclusion criteria. Informed consent will be obtained. Characteristics of patients including age, gender, disease severity, and disease history will be documented during the screening visit.

Five Subjects with Distal Subungual Onychomycosis (mild to moderate DSO) infection of their big toe (hallux) nail infected by the dermatophytes *Trichophyton (T.) rubrum* or *T. mentagrophytes* will be enrolled.

Treatments will be performed at the office of the Investigator as elaborated in the **3.4 Conduct of Study** section below. The treatment protocol outlines three 45-minute treatments over the course of the first week (within 7 calendar days).

Primary study endpoint will be mycological cure, which is defined as two consecutive negative cultures following treatment. Mycological cultures will be collected (1) during screening, (2) after the third treatment, and (3) around a week (5-15 calendar days) after the third treatment.

CONFIDENTIAL

Secondary study endpoint will be clear nail growth. Photographs of the target toes will be taken throughout the study to track clear nail growth.

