3.4.1.4 Discontinuation

If an eligible Subject drops out of the study for any reason, the Investigator must make every reasonable effort to obtain clinical assessments of adverse events. All data should be recorded in the CRF for the Subject and the reason for the drop out should be documented.

In the event that a Subject drops out of the study due to an adverse event, the nature of the event and its clinical course must be fully documented. The Investigator must attempt to follow the Subject until the adverse event has resolved, become clinically insignificant, stabilized, or the Subject is lost to follow-up.

Subjects who drop out of the study without completing the three 45-minute treatments over the course of the first week (within 7 calendar days) will be considered premature drop out. The Sponsor will take reasonable action to replace any of the Subjects who drop out prematurely to maintain the 5-Subject enrollment.

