3.4.2.1 Screening Visit – Baseline

- Obtain Subject's written informed consent prior to initiating any study procedures.
- Document Subject's Informed Consent in the Subject's medical record.
- Screen potential Subject according to the study inclusion/exclusion criteria.
- Take the Subject's medical history.
- Perform a brief physical exam.
- Perform urine pregnancy test on women of childbearing potential.
- Photograph the infected hallux nail(s).
 - If both hallux nails are infected and meet the inclusion/exclusion criteria, both nails can be photographed and tested for KOH and mycology. If both are positive for KOH and culture, the Investigator will choose one and only treat that one in the study.
- Perform KOH testing of infected hallux nail(s): Before obtaining a specimen, make sure the nail is clipped and cleansed with an alcohol swab to remove bacteria and debris.
- Collect mycology sample for lab culture: Prepare and ship the mycology samples according to the instructions from the designated mycology laboratory.

3.4.2.2 Study Visit 1 - Day 1

- Check for conformance to inclusion/exclusion criteria.
- Perform debridement on the infected nail to be treated.
- Notch the nail.
- Measure distance between proximal nail fold and notch.
- Insert the Disposable into the RenewalNail™ plasma treatment device.
- Brush the top, edges, and underside of the infected nail with the Nail Penetration Enhancer.
- Insert the Subject's foot into the opening of the Disposable that was placed the device.
- Ensure that the Subject's foot is properly inserted into the device with a seal of the Disposable flexible material around the foot.
- Push the device power button to start the treatment.
- Complete the 45-minute plasma treatment.
- Perform clinical evaluation of the toes after plasma treatment as specified in “5.0 Safety Assessment/Risks”
- Check on occurrence of adverse events. Stop protocol if any serious adverse events occur.
- Photograph the treated nail.

3.4.2.3 Study Visit 2

Study Visit 2 should occur no sooner than 36 hours after Study Visit 1. In no circumstance should the Subject receive treatment on two (2) consecutive days.

- Check on occurrence of adverse events.
- Perform a plasma treatment per instructions in the *Instructions for Use of the DeviceFarm RenewalNail Plasma Generator DFPD-003* document.
- Perform clinical evaluation of the toes after plasma treatment as specified in “5.0 Safety Assessment/Risks”
- Photograph the treated nail.

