3.4.2.4 Study Visit 3

Study Visit 3 should occur no sooner than 36 hours after Study Visit 2, but within 7 calendar days from Study Visit 1. In no circumstance should the subject receive treatment on two (2) consecutive days

- Check on occurrence of adverse events.
- Perform a plasma treatment per instructions in the *Instructions for Use of the DeviceFarm RenewalNail Plasma Generator DFPD-003* document.
- Perform clinical evaluation of the toes after plasma treatment as specified in “5.0 Safety Assessment/Risks”
- Perform fungal scrapings for mycological culture as instructed by the laboratory.
- Photograph the treated nail.

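### The Visit 4 culture that completes the primary endpoint has two stated windows (5-15 days after the third treatment, or Day 9-15 from Visit 1), and they disagree at both ends

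*Protocol*

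**What the plan says.** **Window in the design section.** Protocol 3.1 lists three culture times. The last is "around a week (5-15 calendar days) after the third treatment".

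**Window in the visit schedule.** Protocol 3.4.2.5 is headed "Study Visit 4 - Day 12 (+/- 3 days". Section 3.4.2.2 sets Visit 1 as Day 1, so this is Day 9 to Day 15.

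**Same sample.** Section 3.4.1.3 names the Visit 4 culture as the second of the two used to assess mycological cure. Section 9.0 defines cure as negative results at Visit 3 and Visit 4 and states no interval between them.

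**Wording in the objectives.** Section 2.0 says "Mycological cure will be assessed with two consecutive mycological culture tests done over a week".

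**Timing of the third treatment.** Section 3.4.2.3 says "Study Visit 2 should occur no sooner than 36 hours after Study Visit 1" and adds "In no circumstance should the Subject receive treatment on two (2) consecutive days". Section 3.4.2.4 says "Study Visit 3 should occur no sooner than 36 hours after Study Visit 2, but within 7 calendar days from Study Visit 1" and repeats the ban on consecutive days. Section 3.1 says "The treatment protocol outlines three 45-minute treatments over the course of the first week (within 7 calendar days". Section 3.4.1.4 treats as a premature drop-out a Subject who leaves "without completing the three 45-minute treatments over the course of the first week (within 7 calendar days".

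**The concern.** One section counts the window from the third treatment and the other from the first. The third treatment has no fixed day, so the two windows move relative to each other, and neither section refers to the other or says which governs.

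The Visit 3 culture is taken on the day of the third treatment, and the Visit 5 culture is for reinfection or recurrence. Visit 4 is therefore the only endpoint culture with any interval off treatment. If a site can follow the visit schedule exactly and still sample earlier than 3.1 allows, Subjects are classified as cured or not at intervals the design section rules out. Conversely, a Subject sampled as 3.1 allows can be recorded as off schedule. With five Subjects reported as listings, each classification is itself a result of the study.

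**Working it through.** **Inputs.** Visit 1 = Day 1 (3.4.2.2). Treatments are at least 36 hours apart and never on consecutive days (3.4.2.3, 3.4.2.4). Visit 4 is Day 12 ± 3 (3.4.2.5), or 5 to 15 days after the third treatment (3.1).

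**Step 1: permitted days for Visit 3 (V3).** Treatments must be at least 2 calendar days apart, so Visit 2 is Day 3 at the earliest and Visit 3 is Day 5 at the earliest. The latest day depends on the reading. A first week of 7 calendar days (3.1, 3.4.1.4) ends on Day 7. Seven calendar days from Visit 1 (3.4.2.4) can also be read as 1 + 7 = Day 8. Day 5-7 is the main case, and Day 8 is shown separately.

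**Step 2: can the schedule's window be derived from 3.1?** The schedule gives 12 − 3 = 9 to 12 + 3 = 15, a span of 7 days. Section 3.1 gives V3 + 5 to V3 + 15, a span of 11 days. The spans differ, so no Visit 3 day makes the windows coincide.

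**Step 3: compare them by Visit 3 day.** The gap under 3.4.2.5 runs from 9 − V3 to 15 − V3.

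| V3 | 3.1 window | Gap allowed by 3.4.2.5 | Days meeting both | Schedule days with gap below 5 | 3.1 days after Day 15 | Gap at nominal Day 12 |
|---|---|---|---|---|---|---|
| Day 5 | Day 10-20 | 4-10 | Day 10-15 (6) | 1 | 5 | 7 |
| Day 6 | Day 11-21 | 3-9 | Day 11-15 (5) | 2 | 6 | 6 |
| Day 7 | Day 12-22 | 2-8 | Day 12-15 (4) | 3 | 7 | 5 |
| Day 8, if allowed | Day 13-23 | 1-7 | Day 13-15 (3) | 4 | 8 | 4 |

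**Step 4: totals for Visit 3 on Day 5-7.**
- Pairs permitted by 3.4.2.5: 3 × 7 = 21. Gap below 5 days: 1 + 2 + 3 = 6.
- Pairs permitted by 3.1: 3 × 11 = 33. After Day 15: 5 + 6 + 7 = 18.
- Pairs meeting both: 6 + 5 + 4 = 15. Check: 21 − 6 = 15 and 33 − 18 = 15.

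**Step 5: totals if Day 8 is allowed.**
- Below 5 days: 6 + 4 = 10 of 28. After Day 15: 18 + 8 = 26 of 44.
- Pairs meeting both: 15 + 3 = 18. Check: 28 − 10 = 18 and 44 − 26 = 18.

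**Step 6: spacing of the two endpoint cultures.** The first is taken on the third-treatment day, so the spacing equals the gap above: 2 to 10 days, or 1 to 10 with Day 8. Section 2.0 describes this spacing as a week.

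**The case against.** **Overlap.** The windows are not mutually exclusive. For Visit 3 on Day 5-7, between 4 and 6 study days satisfy both, and nominal Day 12 always does. This is true, but no section tells a site to stay within the overlap.

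**The upper end is only a tighter limit.** A site that follows 3.4.2.5 is never more than 10 days after treatment, so it cannot breach the 15-day maximum. This stands as far as it goes: the conflict in which following the schedule breaks 3.1 is at the lower end. At the upper end the inconsistency affects a site that relies on 3.1.

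**Day 8 is a strained reading.** Sections 3.1 and 3.4.1.4 support Day 7, and 3.4.2.4 can be read the same way. That is fair, so the Day 8 figures are conditional. The finding does not depend on them.

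**Section 2.0 sets no limits.** Also fair. It is loose wording to align, not a third window.

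**The endpoint is not ambiguous.** Section 9.0 names the two visits and excludes no out-of-window sample. That is correct, and it means an early sample counts in full.

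**Five Subjects and no inference.** There is no estimate or test to bias. However, the inconsistency concerns when the primary endpoint is measured, which matters to each listed classification and to deviation reporting.

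**A study-day window could also be made consistent.** In principle it could. With Visit 3 on Day 5-7, a fixed window respects 3.1 for every Subject only if it lies within Day 12 (7 + 5) to Day 20 (5 + 15). The interval off treatment would still vary with the Visit 3 day.

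**Conclusion.** The concern holds and should be fixed. For every permitted Visit 3 day, and on either reading of the 7-day limit, 3.4.2.5 admits cultures earlier than 3.1 allows and excludes later ones that 3.1 accepts. A site exactly on schedule can take the culture 2 to 4 days after the last treatment (1 to 4 if Day 8 is allowed), against a stated minimum of 5.

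This assumes that study days count from Visit 1 = Day 1 and that whole calendar days are compared. The pair counts describe permitted days, not how often such samples will occur. The protocol gives no reason for the 5-day minimum, so no effect on culture results is claimed, and the text does not show which window was intended.

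**What to change.** - Reconcile 3.1 and 3.4.2.5 into one Visit 4 window counted from the actual date of the third treatment, the anchor 3.1 already uses. State an explicit minimum and maximum, chosen by the sponsor, and align the wording in 2.0.
- Reconcile the Visit 3 limit across 3.1, 3.4.1.4 and 3.4.2.4, so that the latest permitted day is a single study day stated the same way in all three. Which day that is remains the sponsor's decision.
- Optionally, show the actual days from Visit 3 to Visit 4 beside each culture result in the Subject listings.

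**Cost.** Wording changes in five sections (2.0, 3.1, 3.4.1.4, 3.4.2.4 and 3.4.2.5), approved by the IRB as 9.2 requires for any change in conduct. No visit or sample is added. If the sponsor keeps a 5-day minimum, sites lose 1 to 3 days at the early end of the present schedule (4 if Visit 3 may fall on Day 8).

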3.4.2.6 Study Visit 5 - Day 42 (+/- 3 days)

- Check on occurrence of adverse events.
- Perform fungal scrapings for mycological culture as instructed by the laboratory.
- Measure nail growth (renotch, if needed)
- Photograph the treated nail.

3.4.2.7 Study Visit 6 - Day 168 (+/- 5 days)

- Check on occurrence of adverse events.
- Measure nail growth
- Photograph the treated nail.

3.4.3 After-Treatment Instructions

After-treatment care will be discussed in detail with each Subject as follows:

- Nail polish or gels should not be applied to treated nails between treatments.
- Do not pick at the treated nail or the skin surrounding the nail.
- Do not use abrasive cleansers, exfoliants, or scrubs on the treated nail or skin around the nail.

4.0 EFFICACY ASSESSMENT

4.1 Photographic Documentation

Baseline photographs will be taken of the infected nails at the Screening Visit prior to KOH and mycology sampling since these sampling procedures require much of the infected nail to be removed in order to reach the site of active infection.

Photographs will be taken of the treated nail at the end of each Study Visit to document the appearance

CONFIDENTIAL

of the nail following each visits' procedures and to allow for photographic assessment of clear nail growth over the course of the study.

All photographs should be done with the digital camera provided by the Sponsor and following the instructions provided in the *Instructions for Use of the DeviceFarm Nail Photography* document.

4.2 Mycological Cure Assessment

Mycological culture assays will be performed at an accredited mycology laboratory after Investigator has acquired a specimen of subungual debris obtained from the area as close to the cuticle as possible. This specimen will be shipped to the mycological lab according to the laboratory instructions. A mycological cure is defined as two consecutive negative cultures following completion of the week of treatment.

5.0 SAFETY ASSESSMENT/ RISKS

Safety will primarily be measured by the occurrence of adverse events. Adverse Events will be assessed at every study visit.

Possible risks from the RenewalNail™ plasma treatment system include: edema, erythema, heat, discomfort, itching, or blistering. The use of the Device is not expected to present any new or different risks to those known to be associated with other FDA approved plasma devices for skin resurfacing or for other energy-based onychomycosis treatments such as lasers.

CONFIDENTIAL

Clinical evaluations of treated toes will be assessed at each visit, using scores for each of the two parameters (erythema and edema); each parameter will be rated as none, mild, moderate or severe (0-3) by the investigator.

Definitions:

Sign/Symptom	Description
Erythema	Redness around the toe(s)
Edema	Swelling around the toe(s)

Signs and Symptoms Scoring:

Score	Assessment	Description
0	None	Absent; symptom not present
1	Mild	Slight, barely perceptible; symptom does not interrupt normal daily activities nor does it require medical management
2	Moderate	Distinctive presence; symptom causes some interruption of normal daily activities but does not require medical management
3	Severe	Marked, intense; symptom interrupts normal daily activities and requires some medical management

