5.1 Adverse Events

An adverse event (AE) is any unfavorable and unintended sign, symptom, or disease temporally associated with the use of a medicinal product, whether or not considered related to the treatment.

Each subject will be monitored for the occurrence of AEs, including SAEs, immediately after treatment initiation. At each visit, the investigator or other site staff will question the Subject about adverse events using an open question taking care not to influence the Subject's answers (e.g., "Have you had any medical problems since your last visit?").

Any adverse event, whether or not it is related to the treatment procedure, will be reported on the Adverse Event form along with the date of onset, the severity, the relationship to the treatment, and the outcome. Under certain circumstances, additional information may be requested.

When an adverse event persists at the end of the study, the Investigator will ensure a follow-up of the Subject until the Investigator agrees the event is satisfactorily resolved or no further follow-up is required. The study requires that Subjects be actively monitored for adverse events up to and including 14 days after last day of the study.

The severity of an adverse event will be scored according to the following scale:

Score _____ Interpretation _____

CONFIDENTIAL

1	Mild	Awareness of sign or symptom, but easily tolerated
2	Moderate	Discomfort enough to cause interference with usual activity
3	Severe	Incapacitation with inability to perform usual activity

The relationship of an adverse event to RenewalNail™ plasma treatment is to be assessed according to the following definitions:

Not related – no temporal association, or the cause of the event has been identified, or the RenewalNail™ plasma treatment cannot be implicated based upon available information.

Possibly related – temporal association, but other etiologies are likely to be the cause. However, involvement of the RenewalNail™ plasma treatment cannot be excluded, based upon available information.

Probably related – temporal association, other etiologies are possible, but unlikely, based upon available information.

Related – established temporal or other association to the event is not reasonably explained by the Subject's known clinical state or any other factor, based on available information.

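### Four of the six device risks named in section 5.0 are never systematically asked about or scored, so the patient-comfort question in section 2.0 has no dedicated data

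*Protocol*

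**What the plan says.** Protocol section 5.0 lists six effects: "Possible risks from the RenewalNail™ plasma treatment system include: edema, erythema, heat, discomfort, itching, or blistering". It then describes the clinical evaluation of the treated toes as "using scores for each of the two parameters (erythema and edema", each rated 0 to 3 by the investigator. The procedure lists for Visits 1 to 3 (sections 3.4.2.2 to 3.4.2.4) send the site back to section 5.0 for the evaluation after each session.

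The toe scores are not the main safety measure: "Safety will primarily be measured by the occurrence of adverse events". Under section 5.1, site staff "will question the Subject about adverse events using an open question", and the example given is "Have you had any medical problems since your last visit". An event, related or not, "will be reported on the Adverse Event form along with the date of onset, the severity, the relationship to the treatment, and the outcome". On grading, "The severity of an adverse event will be scored according to the following scale", and the scale runs from 1 to 3. Section 9.1 tabulates adverse events by type, severity, duration and frequency.

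Section 2.0 includes this secondary question: "Are there treatment protocol or instrument changes that would improve the treatment results, patient safety, or patient comfort".

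**The concern.** The sponsor names six local effects that it considers possible, then gives two of them a scheduled rating. Both are signs that the investigator observes. Nothing that the subject feels is scored, although three of the other four effects (heat, discomfort, itching) are mainly felt and the study asks about comfort.

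An open, non-leading question suits unexpected events. It is a weaker tool for an expected, short-lived sensation during a 45-minute session, because the subject must both recall it and regard it as a medical problem. With five subjects and results shown as listings (section 9.0), the record of each session is the result. If that record is blank for heat or discomfort, the reader cannot tell whether the effect was absent or was not asked about. Section 6.0 itself says that information on the safety of plasma treatment for this infection is limited, so tolerability is a natural product of an early feasibility study.

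**Working it through.** The plan gives no figure to reproduce here. The check is a count, followed by a trace of each route by which an effect could reach the data.

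**Count (section 5.0).** Named risks: 6. Scored in the toe evaluation: 2. Not scored: 6 - 2 = 4 (heat, discomfort, itching, blistering).

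**Order of procedures at the treatment visits (sections 3.4.2.2 to 3.4.2.5).**

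| Session | Listed after the session, same visit | Next listed adverse event check |
|---|---|---|
| Visit 1 | Toe evaluation, adverse event check, photograph | Same visit |
| Visit 2 | Toe evaluation, photograph | Visit 3, at least 36 hours later |
| Visit 3 | Toe evaluation, scrapings, photograph | Visit 4, Day 12 +/- 3, so Day 9 to Day 15 |

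At Visits 2 and 3 the adverse event check comes before the plasma treatment in the list. If all 5 subjects complete all 3 sessions:

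- sessions: 5 x 3 = 15
- sessions with no adverse event check listed after them at the same visit: 5 x 2 = 10

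For those 10, what was felt during the session depends on the general monitoring statement in section 5.1 or on recall at the next visit.

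**Other routes.**

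- *Felt effects (heat, discomfort, itching).* Section 5.1 calls for monitoring once treatment has started, and section 7.3 puts each session under the investigator's supervision. Neither assigns an item, a time point or a form to these sensations.
- *Blistering.* It is visible, and the investigator examines the toes after each session. It is likely to be seen if present at that moment, but it has no line on the score and so no recorded zero.
- *Comfort.* No visit list from screening to Visit 6 has a comfort or tolerability item. No endpoint or analysis in the protocol is tied to the comfort part of section 2.0. The optional sponsor observation in section 8.1 concerns the performance of the instrument.

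**What a blank means.** For erythema and edema a score of 0 is an observation. For the other four effects the plan has no equivalent of 0: only a positive report leaves a trace.

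**The case against.** The best reply is that adverse events, not toe scores, are the primary safety measure, and that any unfavorable sign or symptom qualifies as one. Tolerable itching or warmth has a place at grade 1, and the grade 2 definition refers to discomfort itself. Onset, causality and outcome are recorded and the events are tabulated. Sessions are supervised, the toes are examined after each one, the nail is photographed at every study visit, and the quoted question is only an example of wording. Section 5.0 never promises to score every listed risk.

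Most of this stands, and it rules out two stronger readings.

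- A reader might infer that the four effects have no structured or graded measure. The documents do not support that: once reported, they are graded 1-3 with causality. Counting 15 x 4 = 60 missing scores would likewise ignore this route and would only count cells on a form that the plan does not contain.
- A reader might infer that the comfort question cannot be answered. It is an exploratory question with no threshold, and adverse event reports, supervision and sponsor observation can inform it to some degree.

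It is also fair that the protocol gives no evidence on how often subjects would fail to mention such sensations. The point does not need that rate. What the reply leaves untouched is that nobody is required to ask about these effects after a session, so silence carries little information.

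**Conclusion.** The point holds as a gap in solicitation. Four of the six named risks reach the data only if noticed or reported, mainly through an open question, and for 10 of 15 planned sessions the listed check comes before the session. Absence of a report cannot be read as absence of the effect. The weakness is greatest for heat, discomfort and itching, and smaller for blistering because it can be seen. The comfort question in section 2.0 has no dedicated data and is weakly supported, which is less than saying that it is unanswerable.

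Nothing here is a contradiction or a numerical error, and the primary endpoint is not affected. It is a cheap improvement worth making before enrollment. A later analysis plan could not recover sensations that were never asked about.

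This rests on two assumptions: that all five subjects complete three sessions, and that the case report form and the device instructions, which are not shown, do not already prompt for tolerability.

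**What to change.** At the clinical evaluation already scheduled after each of the three sessions:

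1. Add blistering as a sign rated by the investigator.
2. Add a subject-reported 0-3 rating of heat, discomfort and itching for the session just completed. Write anchors that fit sensation while seated for treatment. The present section 5.0 anchors turn on interference with daily activities and need for medical management, and do not fit this use.
3. State in section 5.0 that any finding meeting the section 5.1 definition is also recorded on the Adverse Event form, so that a solicited score neither replaces nor silently duplicates an event.
4. List the solicited scores by subject and session, separately from events raised by the open question, and name them as the data for the comfort question in section 2.0.

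The cost is four more items at an evaluation that already takes place, with no extra visit. The downside is that direct questions will record more mild reactions than an open question alone, which is the reason for the separate listing.

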3.4.1.3 Study Visits 2-6

The Subject reports back to the Investigator's facility for the remainder of treatments. Investigator inquires with Subject regarding compliance, adverse events and for clinical assessment of the treated area of the foot.

Visit 2 and Visit 3 activities will be carried out as specified in 3.4.2.3 and 3.4.2.4, respectively. Mycological culture collected at Visit 3 will be the first of the two consecutive cultures for assessing mycological cure.

Visit 4 activities are specified in 3.4.2.5. Mycological culture collected at this visit will be the second of the two consecutive cultures for assessing mycological cure.

On Visit 5, mycological cultures will be collected to measure rates of reinfection/recurrence. Visit 5 activities will be carried out as specified in 3.4.2.6.

Visit 6 will be the last visit of the study and activities will be carried out as specified in 3.4.2.7.

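### Erythema and edema scores are required at each visit but missing from the Visit 4-6 procedure lists, and no score is listed before plasma, so a positive score has no earlier value to compare with

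*Protocol*

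**What the plan says.** Section 5.0 sets the requirement: "Clinical evaluations of treated toes will be assessed at each visit, using scores for each of the two parameters (erythema and edema". Each parameter is rated by the investigator from 0 (none) to 3 (severe). The overview in Section 3.4.1.3 points the same way for Visits 2-6, without naming a scale or a time within the visit: "Investigator inquires with Subject regarding compliance, adverse events and for clinical assessment of the treated area of the foot". It then sends the reader to the visit lists for the activities.

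Section 3.4.2 presents those lists as the activities for each visit. The lists for Visits 1, 2 and 3 (Sections 3.4.2.2 to 3.4.2.4) each carry the line "Perform clinical evaluation of the toes after plasma treatment as specified in", with a reference to Section 5.0. At Visit 1 this line comes after "Perform debridement on the infected nail to be treated", after notching, after "Brush the top, edges, and underside of the infected nail with the Nail Penetration Enhancer" and after the 45-minute treatment.

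The lists headed "Study Visit 4 - Day 12 (+/- 3 days", "Study Visit 5 - Day 42 (+/- 3 days" and "Study Visit 6 - Day 168 (+/- 5 days" contain an adverse event check, a photograph and, depending on the visit, scrapings or a growth measurement. None contains a toe evaluation. The Screening list has a brief physical examination and a nail photograph, but no erythema or edema score.

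**The concern.** There are two separate points.

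The first is an inconsistency. The evaluation line appears at three visits and is absent from the other three, so a site or a case report form designer could take the omission as intended. Scoring would then end immediately after the third treatment.

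The second is a gap in the design. No passage promises a score before plasma, so nothing is contradicted. But a single score per treatment visit, always taken after the procedure, does not show what was there beforehand. Following Section 5.0 to the letter does not help, because it does not say when in the visit the score is taken.

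Safety is part of the primary objective (Section 2.0), and Section 5.0 names both erythema and edema as possible device risks. There is no placebo arm, and Section 9.0 plans subject listings rather than summary or inferential statistics. Comparison within a subject, before against after, is therefore the main comparison these scores could support. No later analysis can recover scores that were never taken.

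**Working it through.** The protocol gives no figure of its own here. The check sets the sections side by side and counts.

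Inputs: 5 subjects (Synopsis); 6 study visits, 3 of them with treatment (Section 3.4.2); 2 parameters (Section 5.0). Screening is not counted, since Section 5.0 speaks of treated toes and no toe has been treated by then.

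| Visit | Section 5.0 asks for scores | Section 3.4.2 list | Listed score before plasma |
|---|---|---|---|
| 1 | yes | yes, after debridement, notching, enhancer and plasma | none |
| 2 | yes | yes, after plasma | none |
| 3 | yes | yes, after plasma | none |
| 4 (Day 9-15) | yes | no | not applicable |
| 5 (Day 39-45) | yes | no | not applicable |
| 6 (Day 163-173) | yes | no | not applicable |

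1. Occasions under Section 5.0: 6 × 5 = 30, and 30 × 2 = 60 ratings.
2. Occasions under the lists: 3 × 5 = 15, and 15 × 2 = 30 ratings.
3. Difference: 15 occasions, 30 ratings, all at Visits 4-6.
4. Sessions with a listed score before plasma: 0 of 3 × 5 = 15. In 5 of these (Visit 1) the only score also follows debridement and notching. In the other 10 (Visits 2 and 3) the previous session may be as recent as 36 hours.
5. Time without a listed score if the lists are followed: with at least 36 hours between sessions and no treatment on consecutive days, Visit 3 is Day 5 at the earliest. At the latest it is Day 7 or Day 8, depending on how the 7 calendar days are counted. To Visit 6 this gives 163 − 8 = 155 to 173 − 5 = 168 days.
6. The same span if Section 5.0 is followed: Visits 4 and 5 are scored, but 163 − 45 = 118 to 173 − 39 = 134 days remain between Visits 5 and 6.

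What a score can tell: a 0 after plasma shows that the sign was absent at that time, whatever came before. A positive score at Visit 1 may reflect a pre-existing sign, the nail preparation or the treatment. A positive score at Visit 2 or 3 may also be a residue of the previous session. If the previous post-plasma score was 0, the sign arose after that score, but the scores still do not show which session caused it. The ambiguity is therefore confined to positive scores.

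**The case against.** The strongest reply is that little rests on these scores. Section 5.0 makes adverse events the primary safety measure, both Section 9.1 endpoints are built on them, and no endpoint or decision rule uses the 0-3 scores. An adverse event includes any unfavorable sign, so redness or swelling that the investigator sees can be recorded with onset, relationship, and start and stop times. This stands, and it limits the weight of the point.

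There are also unscored safeguards:
- The Screening physical examination and medical history. Treatment waits for the culture result, so these can precede Visit 1 by about four weeks.
- The eligibility check at Visit 1, listed before debridement. It is not directed at redness or swelling.
- The adverse event checks before plasma at Visits 2 and 3. These use an open question, and a grade 1 sign is by definition barely perceptible, so a subject may not mention it. At Visit 1 the listed check comes after plasma.
- The clinical assessment in Section 3.4.1.3, whose timing relative to plasma is not stated.
- The photographs. They show the nail, whereas the signs are defined around the toe, and at Visits 1-3 they are taken at the end of the visit.

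These give partial information but no score to compare with. The Instructions for Use and the case report form are not shown and may prompt an inspection or a score.

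A reader might infer that the protocol abandons scoring after treatment. It does not: Section 5.0 requires it, the lists are silent rather than prohibiting, and Section 10.2.1 binds the investigator to the protocol's procedures. A reader might also take the 155 to 168 days as months of lost scoring. What the lists drop is three occasions per subject, and full compliance with Section 5.0 still leaves 118 to 134 days between the last two visits.

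**Conclusion.** Both points hold, with modest effect. The Visit 4-6 lists disagree with Section 5.0, at a possible loss of 15 of 30 scoring occasions. Independently, none of the 15 treatment sessions has a listed score before plasma, so a positive score alone cannot be attributed to the session it follows.

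The documents do not support the wider conclusion that the scores are uninterpretable or that device safety cannot be assessed. Zero scores are informative, and adverse event recording continues at every visit. Nor does the ambiguity about new signs follow from the Visit 4-6 omission; it comes only from the timing of scores at Visits 1-3.

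The counts assume 5 subjects completing all six study visits, no Screening score under Section 5.0, and no scoring step in the documents not shown. The change should still be made, because it is small and the information cannot be recovered afterwards.

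**What to change.** (a) At Visits 1, 2 and 3, add one erythema and edema score at the start of the visit, before any procedure; at Visit 1 this means before debridement. Keep the post-plasma score and list both by subject. A further Visit 1 score between nail preparation and plasma is not needed, since the objectives in Section 2.0 evaluate the system and its treatment protocol together.

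(b) Reconcile the Visit 4, 5 and 6 lists with Sections 5.0 and 3.4.1.3 by adding the same two scores, preferably before any scraping or renotching.

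Cost: part (a) adds 3 occasions per subject, so 3 × 5 = 15 occasions and 15 × 2 = 30 ratings, at visits already held. Part (b) adds no ratings beyond the 60 that Section 5.0 already implies, though it does fix when in the visit they are taken. The total becomes 60 + 30 = 90 ratings. The procedure lists and the case report form fields need matching edits.
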